6.3.2.2. Analysis

Weekly average SABA use, change from week 1 in weekly average SABA use and weekly SABA-free days will be summarized using descriptive statistics.

6.3.3. Secondary Endpoint #3 – Usability and Acceptability of the Digital System**6.3.3.1. Definition**

The SUS is used to explore device acceptability and usability for patients in the DS group. It is a 10-item tool that provides a composite measure of the overall usability of the system being studied. Responses for each item range from 1 (strongly disagree) to 5 (strongly agree). To calculate the SUS score, first sum the responses from each item. Each item's contribution will range from 0 to 4. For items 1,3,5,7, and 9 the score contribution is the response minus 1. For items 2,4,6,8 and 10, the score contribution is 5 minus the response. Multiply the sum of the scores by 2.5 to obtain the overall SUS score. SUS scores have a range of 0 to 100.

Secondary endpoint #3 is the assessment of the DS (eMDPI, App and dashboard) acceptability and usability, utilizing the SUS, completed by the patients in the DS group, 18 years of age or older, and investigational center personnel at the end of the study. The SUS will be completed after all other questionnaires.

6.3.3.2. Analysis

The SUS score (completed by patients and investigator sites) at the end of treatment and ET visits will be summarized as continuous data using descriptive statistics.

6.3.4. Secondary Endpoint #4 – Assessment of Behavioral Correlates of Responsiveness to Digital Health Technology**6.3.4.1. Definition**

The BMQ is used to assess cognitive representations of medicine. The BMQ-Specific (BMQ-S11) is an 11-item questionnaire that assesses representation of medication prescribed for personal use. The specific necessity subscale is the sum of items 1, 3, 5, 7, and 10, and the specific concern subscale is the sum of items 2, 4, 6, 8, 9, and 11. The BMQ should be the second questionnaire completed during a study visit following the ACT.

The BIPQ is a 9-item questionnaire designed to rapidly assess cognitive and emotional representations of illness. The BIPQ uses a single-item scale approach to assess perception on a 0-10 response scale. The BIPQ comprises 5 items on cognitive representation of illness perception: consequences, timeline, personal control, treatment control, and identity. There are 2 items on emotional representation: concern and emotions; one item is on illness comprehensibility. The last item is on perceived cause of illness, in which respondents list the 3 most important causal factors in their illness. The cognitive subscale is the sum of items 1 to 5, and the emotional representation subscale is the sum of items 6 and 7. The BIPQ should be the third questionnaire completed during a study visit following the BMQ.

Secondary endpoint #4 is the assessment of patients' beliefs and perceptions about their disease and treatment, utilizing the BMQ and the BIPQ for both the DS and CC groups, patients 18 years of age or older, describing their behavioral profile at baseline and at the end of the study.

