6.1.3. Brief Illness Perception Questionnaire

The BIPQ is a 9-item questionnaire designed to rapidly assess cognitive and emotional representations of illness ([Broadbent et al 2006](#)). The BIPQ uses a single-item scale approach to assess perception on a 0-10 response scale. It is developed by forming one question that best summarizes the items contained in each subscale of the Illness Perception Questionnaire-Revised which has over 80 items. The BIPQ comprises 5 items on cognitive representation of illness perception: consequences, timeline, personal control, treatment control, and identity. There are 2 items on emotional representation: concern and emotions; one item is on illness

comprehensibility. The last item is on perceived cause of illness, in which respondents list the 3 most important causal factors in their illness. For this questionnaire, the general word 'illness' can be replaced by the name of a particular illness such as asthma. The word 'treatment' in the treatment control item can be replaced by a particular treatment such as 'surgery' or 'physiotherapy' (Broadbent et al 2006). The discriminant validity of the questionnaire is supported by its ability to distinguish between different illnesses, namely asthma, diabetes, colds, myocardial infarct prior to discharge, and pre-diagnosis chest pain patients waiting stress exercise testing. The BIPQ will be answered by the patients, 18 years of age or older, at the investigational center at Visit 1, Visit 2, or at the ET visit. The BIPQ should be the third questionnaire completed during a study visit following the BMQ.

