4.3. Handling Withdrawals and Missing Data

For the primary endpoint, patients who discontinue early due to technology failure, disliking the digital platform, disease worsening, adverse experience or disliking the IMP will be counted as treatment failures. For those who discontinue early not to these reasons, the ACT value assessed at ET visit will be used. Those who discontinue early and do not have an ET visit will be counted as treatment failures.

For the SUS items 1, 3, 5, 7, and 9, if response to 1 item is missing, the missing item will be replaced by the average of the remaining 4 responses. For items 2, 4, 6, 8, and 10, if response to 1 item is missing, the missing item will be replaced by the average of the remaining 4 responses. If response to 2 or more of items 1, 3, 5, 7, and 9 are missing, or 2 or more of items 2, 4, 6, 8, and 10 are missing, the overall SUS score will be set to missing.

For the BMQ subscales, if response to 1 item within a subscale is missing, the missing response will be replaced with the average of the remaining responses within the subscale. If response to 2 or more items within a subscale are missing, the missing responses will not be replaced and the subscale score will be set to missing.

For the BIPQ cognitive subscale, if response to 1 item within the subscale is missing, the missing response will be replaced with the average of the remaining responses within the subscale. If response to 2 or more items within the subscale is missing, the missing responses will not be replaced and the subscale score will be set to missing. For the emotional subscale, if 1 of the responses is missing then the subscale will be set to missing.

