6.3.4.2. Analysis

Summary statistics for the BMQ and BIPQ subscales will be presented at baseline, and the end of treatment and ET visits. BMQ and BIPQ subscales values and changes from baseline to each visit will be summarized using descriptive statistics.

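### The BIPQ cognitive score is an unreversed sum that may mix item directions, and no item-level summary is planned to show whether changes offset

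*SAP*

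**What the plan says.** SAP 6.3.4.1 describes the instrument and its scoring: "The BIPQ comprises 5 items on cognitive representation of illness perception: consequences, timeline, personal control, treatment control, and identity". Items are rated 0 to 10. The scoring rule is "The cognitive subscale is the sum of items 1 to 5", so the score runs from 0 to 50. No item is reversed, and no favourable direction is given for the score.

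Protocol 6.1.3 names the same five items and gives no scoring rule. It says: "The BIPQ uses a single-item scale approach to assess perception on a 0-10 response scale".

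SAP 4.3 handles incomplete responses: "For the BIPQ cognitive subscale, if response to 1 item within the subscale is missing, the missing response will be replaced with the average". That average is taken over the other responses in the subscale. Again nothing is said about direction.

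SAP 6.3.4.2 sets the output: "BMQ and BIPQ subscales values and changes from baseline to each visit will be summarized using descriptive statistics". No table of individual BIPQ items is planned.

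For the SUS, by contrast, SAP 6.3.3.1 writes the reversal out: "For items 2,4,6,8 and 10, the score contribution is 5 minus the response". A programmer following the SAP would therefore reverse SUS items and leave BIPQ items as recorded.

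**The concern.** By their names, two of the five items (personal control and treatment control) measure something a patient would want more of. Two others (consequences and identity) measure burden. Timeline is less clear from its name alone, and the documents do not classify it. If ratings run in the direction the names suggest, a plain sum adds a favourable quantity to an unfavourable one.

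A patient who feels more in control and less burdened could then show little or no change. With only the subscale reported, a mean change near zero could reflect either no movement or two opposite movements, and no planned table would tell these apart. The endpoint is meant to describe patients' beliefs and perceptions at baseline and at the end of the study, so that distinction matters to its reader.

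**Working it through.** The plan states no figure on this point, so there is none to reproduce. The check is arithmetic on the stated scoring rule.

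**Inputs.** From SAP 6.3.4.1: five items, each 0 to 10, taken as items 1 to 5 in the order listed (i1 consequences, i2 timeline, i3 personal control, i4 treatment control, i5 identity).

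**Assumption A, from the names only.** Higher i3 and i4 are favourable; higher i1 and i5 are unfavourable. Where timeline needs a direction, higher is treated as unfavourable.

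**Formulas.**
- Plain sum, as in the SAP: S = i1 + i2 + i3 + i4 + i5.
- Aligned sum: L = i1 + i2 + (10 − i3) + (10 − i4) + i5.
- Change in S minus change in L = 2 × (change in i3 + change in i4). The two scores part by twice the total movement on the control items.

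**Uniform improvement of d points under A.**
- Timeline unchanged: S changes by −d + 0 + d + d − d = 0; L changes by −d + 0 − d − d − d = −4d. For d = 1, 2, 3 this is 0 against −4, −8, −12.
- Timeline also falls by d: S changes by −d − d + d + d − d = −d; L changes by −5d. For d = 1, 2, 3 this is −1, −2, −3 against −5, −10, −15.

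**One illustrative patient (invented ratings).** Baseline (7, 8, 4, 5, 7), end of treatment (5, 8, 6, 7, 5).
- S: 31 to 31, change 0.
- L: 7 + 8 + 6 + 5 + 7 = 33 to 5 + 8 + 4 + 3 + 5 = 25, change −8.

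**Extremes under A.** The most favourable profile (0, 0, 10, 10, 0) gives S = 20 and the least favourable (10, 10, 0, 0, 10) gives S = 30. The corresponding L values are 0 and 50. The 10-point gap in S comes entirely from timeline: the other four items contribute 20 to both profiles.

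**Missing item under A.** Take (2, 2, missing, 8, 2).
- SAP rule: (2 + 2 + 8 + 2) / 4 = 3.5 for personal control.
- Aligned first: the observed control item becomes 10 − 8 = 2, the mean is (2 + 2 + 2 + 2) / 4 = 2, which is 10 − 2 = 8 on the recorded scale.
- The fill for a missing control item draws on one control item, two burden items and timeline. For a missing burden item it draws on one burden item, two control items and timeline. Either way the mean mixes directions.

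**The other end of the range.** If both control items are worded or stored so that higher means less control, S is already aligned for the four classified items. Nothing cancels among them, and reversing the control items would create the fault.

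**The case against.** The strongest objection is that the argument turns on anchors the documents do not print. The direction of each item is inferred from a one- or two-word name, and the scoring source that the protocol cites is not available here. This stands. It is why the effect has to be given as a range, from none to full cancellation, and why reversal cannot be recommended unconditionally.

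Exact cancellation also needs equal and opposite movement with timeline still. That is a chosen case, and nothing in the documents says how common it would be. This stands too, although unequal movements would still partly offset under assumption A.

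Protocol 6.1.3 itself groups these five items as cognitive, so a subscale built on them is not arbitrary. That is fair, but a shared heading does not show that the items point the same way.

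A reader might infer that the SAP fills a missing item only from items of opposite direction. It does not: the average is over all the remaining items in the subscale, one of which shares the missing item's direction when a control, consequences or identity item is missing.

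A reader might also infer that endpoint #4 cannot describe patients' beliefs and perceptions at all. The documents do not support that. The two BMQ subscales and the BIPQ emotional subscale are scored separately and are untouched.

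**Conclusion.** The textual part is firm: the cognitive score is a plain sum, no BIPQ item is reversed in either document, no favourable direction is given, and only subscales are reported. Whether changes actually cancel is conditional. Under the direction the names suggest, the loss runs up to the whole signal on the four classified items (0 instead of −4d); with control items recorded the other way it is zero. The documents do not settle which applies, so it would go too far to say that real changes will cancel.

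The reach is small. One of four descriptive subscales in one secondary endpoint is affected. The primary analysis, the sample size and the success criterion do not depend on it. The remedy is nonetheless worth taking, because item-level reporting prevents this offsetting under every reading of the anchors.

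**What to change.** Add to SAP 6.3.4.2 descriptive summaries of each rated BIPQ item, with values at baseline, end of treatment and the ET visit and changes from baseline, using observed responses. This fits the single-item approach in protocol 6.1.3. It would also report the comprehensibility item, which SAP 6.3.4.1 lists but places in neither subscale.

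If the cognitive sum is kept, first state in SAP 6.3.4.1 the 0 and 10 anchors as recorded and the favourable direction of every item, including timeline. Then align the items, for example with 10 minus the response for the two control items if higher means more control. Do this before summing and before applying the missing-item rule in SAP 4.3.

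The cost is SAP wording and a few table rows. The responses are already to be collected, and SAP 2.5.2 allows for amendments approved before database lock.

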6.3.4.2. Analysis

Summary statistics for the BMQ and BIPQ subscales will be presented at baseline, and the end of treatment and ET visits. BMQ and BIPQ subscales values and changes from baseline to each visit will be summarized using descriptive statistics.

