9.5.4.3. Secondary Analysis

All summaries of all secondary endpoints will be based on the mITT analysis set and analyzed descriptively.

For continuous variables, descriptive statistics (number [n], mean, standard deviation, median, minimum, and maximum) will be provided for observed values and changes from baseline to each time point. For categorical variables, patient counts and percentages will be provided.

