9.5.4.4. Other Analyses

No other analyses are planned.

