The secondary objective (#4) is to assess behavioral correlates of responsiveness to digital health technology among patients for all patients in both groups.	This secondary endpoint is the assessment of patients' beliefs and perceptions about their disease and treatment, utilizing the Beliefs about Medicines Questionnaire (BMQ) and the Brief Illness Perception Questionnaire (BIPQ) to both the DS and CC groups, patients 18 years of age or older, describing their behavioral profile at baseline and at the end of the study.
The secondary objective (#5) is to evaluate the safety of Albuterol eMDPI.	This secondary endpoint is the reporting of adverse events related to Albuterol eMDPI at participating investigational centers. The safety endpoints for this study include the following for all patients in both groups: 
• adverse event data• adverse device effect data

Notes: The Digital System (DS) group will include eligible study population patients who will use the DS (eMDPI, App, DHP [Cloud solution], and dashboard) during the treatment period. The concurrent control (CC) group will include eligible patients who will be treated with their standard of care albuterol-administering rescue inhalers and will not use the DS during the treatment period.

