6. DATA ANALYSIS

6.1. General

The efficacy of the drug product will not be evaluated in this study. The focus of this study is the engagement of the patient with the Albuterol eMDPI DS.

The mITT analysis sets will be used for all data analyses. Summaries will be presented by treatment group, as randomized.

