6.2.2. Primary Analysis

To analyze the primary endpoint, the following estimand framework will be used:

1. Analysis will be performed on the mITT analysis set.
2. A binary distribution is assumed for the primary endpoint. Patients who discontinue early due to technology failure, disliking the digital platform, disease worsening, adverse experience or disliking the IMP will be counted as treatment failures. For those who discontinue early not due to these reasons, the ACT value assessed at the ET visit will be used.
3. Summary measure: A successful differentiation between the 2 groups will be determined by a Bayesian posterior probability for $\beta_1 > 0$ greater than 0.95 (1-sided). The following statistical methods will be utilized:

Logistic regression model allowing for different response rates at enrolling investigational centers will be used for testing the hypothesis $H_0: \beta_1 = 0$, $H_1: \beta_1 > 0$ in the following model:

$$\ln\left(\frac{p_{ij}}{1-p_{ij}}\right) = \beta_0 + \beta_1 x_i + \beta_2 \text{baseline ACT value} + \text{Center}_j$$

where x_i = treatment group i , p_{ij} = response proportion of treatment group i at Center j , $Center_j$ = random center effect of center j .

Non-informative priors will be assumed for all coefficients. Estimates of mean response rate and corresponding 95% credible intervals for individual proportions, histograms of the posterior response rates, odds ratio with corresponding 95% credible intervals for DS versus CC, and probability of ($\beta_1 > 0$) and probability of (*Odd Ratio* > clinical meaningful value) will be presented.

The SAS code for the primary analysis is as follows:

```
proc mcmc data = x nbi = 1000 nmc = 500000 thin = 20 seed = 159 outpost =
post1 monitor = (beta0-beta2 sigma2 beta1_gt0 pi pi0 pooled or)
statistics=(summary intervals);
parms beta0-beta2 0;
parms sigma2 1;
prior beta0-beta2 ~ normal(mean = 0, var = 1000);
prior sigma2 ~ igamma(shape = 0.001, scale = 0.001);
random b0 ~ normal(mean = 0, var = sigma2) subject = CENTER;
eta = beta0 + b0 + beta1*trt + beta2*y0;
pi = logistic(eta);
pi0 = logistic(beta0 + b0 + beta2*y0);
model count ~ binomial(n = total, p = pi);
array or[<# of sites>];
or[1] = exp(b0 + beta1);
pooled = exp(beta1);
beta1_gt0 = beta1 > 0;
run;
```

where count = number of responders and total = number of patients.

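### Secondary objective #4 asks for behavioral correlates of responsiveness, but neither its endpoint nor its visible analysis links belief scores to response

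*SAP*

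**What the plan says.** **Objective.** Protocol 2.1 and SAP 1.1 give secondary objective #4 as to "assess behavioral correlates of responsiveness to digital health technology among patients for all patients in both groups". The heading of SAP 6.3.4 repeats the idea.

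**Endpoint.** Protocol 9.5.2 and SAP 6.3.4.1 define the endpoint as an assessment of beliefs and perceptions with the BMQ and BIPQ in adults of both groups, "describing their behavioral profile at baseline and at the end of the study". It contains no response variable.

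**Analysis.** SAP 6.3.4.2 has two sentences: "Summary statistics for the BMQ and BIPQ subscales will be presented at baseline, and the end of treatment and ET visits", and "BMQ and BIPQ subscales values and changes from baseline to each visit will be summarized using descriptive statistics". For grouping, SAP 6.1 says: "Summaries will be presented by treatment group, as randomized".

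**Other visible text.** Protocol 9.5.4.3 says: "All summaries of all secondary endpoints will be based on the mITT analysis set and analyzed descriptively". Protocol 9.5.4.4 says: "No other analyses are planned". The linear predictor of the primary model in SAP 6.2.2 is "eta = beta0 + b0 + beta1*trt + beta2*y0", that is, treatment, baseline ACT and a random center effect. The sensitivity model in SAP 6.2.3 has treatment and baseline ACT only. The exploratory objectives, endpoints and analyses (Protocol 2.2, 9.5.3 and 9.5.4.5; SAP 1.2 and 6.4) are redacted or blank in the public versions.

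**The concern.** A correlate of responsiveness is a statement about two variables measured on the same person. The endpoint and analysis attached to this objective carry only one of them. Randomization makes baseline belief means equal between arms in expectation, so the baseline comparison is uninformative. A mean change in belief by arm does not show which patients responded.

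Showing both arms also matters. Beliefs that go with improvement under the digital system (DS) may go with improvement under usual care (CC) as well. That would be ordinary prognosis, not responsiveness to the technology. The CC questionnaires make that comparison possible, but the visible plan does not call for it.

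At stake is one secondary objective. It may be reported with tables that do not address it, or be answered after the data are seen, with the subscale, the cut-point and the meaning of response all open to choice.

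**Working it through.** **1. Objective against planned output.**

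| Needed for a correlate of responsiveness | In the visible plan? |
|---|---|
| Belief score per patient | Yes: BMQ necessity and concern, BIPQ cognitive and emotional (SAP 6.3.4.1) |
| Definition of responsiveness for this objective | No |
| Belief score by response (table, correlation or model term) | No: SAP 6.3.4.2 and 6.1 give arm and visit only |
| Belief term or interaction in a response model | No: SAP 6.2.2 and 6.2.3 have none |
| Same-patient data on both variables | Yes: adults complete ACT, BMQ and BIPQ at the same visits (Protocol Table 3) |

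SAP 4.4 summarizes the ET visit separately, so early leavers appear on their own line. That is not a responder split. Under SAP 4.3 some early leavers are failures by rule and others are classified by their ET ACT value.

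**2. Why arm-level summaries do not suffice.** Take 150 DS patients with the plan's 73% response. Suppose, as an invented example, that half (75) hold a high belief score.
- No link: 0.73 × 75 = 54.75 expected responders in each half, total 109.5, or 73%.
- Strong link: all 75 high scorers respond, as do 34.5 of the 75 low scorers (46%). The total is again 109.5, or 73%.

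The distribution of belief scores and the response rate are identical in both cases. Only the cross-classification separates them.

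**3. The plan's own figure.** The only power figure in the documents is 0.77 for the primary endpoint (SAP 2.4: 150 per group, 60% against 73%, analogous to one-sided 0.05). With the pooled proportion 0.665:

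z = [0.13 × √150 − 1.645 × √(2 × 0.665 × 0.335)] / √(0.60 × 0.40 + 0.73 × 0.27) = (1.592 − 1.098) / 0.661 = 0.748, so power = 0.773.

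This reproduces 0.77. It confirms the inputs used next but has no bearing on objective #4.

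**4. Precision if an interaction were estimated.** For a subscale scaled to SD 1 and only weakly related to response, ignoring center and baseline ACT, with n contributing adults per arm:

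SE(log ratio of odds ratios) = √[1/(n × 0.60 × 0.40) + 1/(n × 0.73 × 0.27)]; interval factor = exp(1.96 × SE).

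| n per arm | Share of 150 (assumed) | SE | 95% factor |
|---|---|---|---|
| 150 | 100% | √(0.02778 + 0.03382) = 0.248 | 1.63 |
| 127 | 85% | 0.270 | 1.70 |
| 120 | 80% | 0.277 | 1.72 |

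An estimate at the null would have limits of about 1/1.63 = 0.61 to 1.63 with everyone contributing, and 1/1.72 = 0.58 to 1.72 at 80%. For 80% power at two-sided 5%, the ratio of odds ratios per SD would have to be about exp(2.80 × 0.248) = 2.0 to exp(2.80 × 0.277) = 2.2. The documents do not give the share of adults who will complete the questionnaires.

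**The case against.** The strongest reply is that SAP 6.3.4.2 does what the endpoint asks. The endpoint is a profile at two time points, the protocol commits to descriptive analysis of secondary endpoints, and the SAP delivers descriptive summaries. This stands: the analysis section does not contradict its endpoint. It moves the defect without removing it, because endpoint and analysis together still do not serve the stated objective.

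Second, a reader might infer that the trial nowhere relates beliefs to response. The documents do not support that, because the exploratory sections are redacted. What can be said is that the visible text for objective #4 contains no such analysis and points to none.

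Third, a reader might infer that the objective cannot be answered. That is true of the planned outputs but not of the data, which are collected on the same adults in both arms. Protocol 9 also allows additional analyses if they are disclosed in the study report. What would be lost is prespecification.

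Fourth, a formal interaction model goes beyond the protocol's descriptive commitment, and its intervals, spread over four subscales, would settle little. This also stands. The objective speaks of correlates, and responsiveness is undefined, so the documents do not require an interaction model. A responder table is itself descriptive and is enough to begin answering the question.

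**Conclusion.** The concern holds in this form: objective #4 asks for correlates of responsiveness, while its endpoint and its visible analysis give a belief profile by arm and visit with no link to response. Followed exactly, the planned outputs for this objective do not address it. The conclusion rests on reading the text, not on a calculation, and is limited to the visible sections.

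The weight is moderate. This is one secondary objective in a feasibility study, and no success rule, sample size or safety conclusion depends on it. It is still worth settling before database lock, because the repair is cheap and later choices would be open to selection. If an interaction is added, its precision is about times or divided by 1.6 to 1.7 per SD, under the assumptions that 80-100% of 150 per arm contribute, response is 60% and 73%, and center and baseline ACT are ignored. That is adequate for an exploratory estimate and not for a claim.

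**What to change.** In SAP 6.3.4.2:

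1. Define responsiveness for this objective as primary-endpoint (ACT) responder status, derived as in SAP 6.2.1 and 4.3.
2. For patients 18 or older, tabulate baseline BMQ necessity, BMQ concern, BIPQ cognitive and BIPQ emotional scores by arm and responder status. Show both arms, so that an association in DS can be read against ordinary prognosis in CC. Use baseline scores, since end-of-treatment scores are measured after the intervention.
3. Optionally, for each subscale, add the standardized baseline score and its interaction with treatment to the primary model. Report the interaction odds ratio with a 95% credible interval, labelled exploratory, with no success claim.

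If only a profile is intended, reword the objective (Protocol 2.1 and synopsis, SAP 1.1) and the SAP 6.3.4 heading to describing beliefs and perceptions, and leave the analysis as it is.

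Cost: the first route needs SAP wording and a small amount of programming on data already collected, with no new visits or patients. SAP 2.5.2 allows amendments before database lock. The optional models bring wide intervals that must be presented as such. The rewording route also touches the protocol.
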